EQD ₂	Equivalent Dose in 2 Gy fractions
FLIE	Functional Living Index - Emesis
GCP	Good Clinical Practice
GTV	Gross Tumour Volume
HCP	Health Care Provider
HRQoL	Health Related Quality of Life
ICF	Informed consent form
ICH	International Council for Harmonization

IGRT	Image Guided Radiation Therapy
IRB	Institutional Review Board
KT	Knowledge Translation
kV	Kilo-Volt
MF	Multi Fraction
MLC	Multi-Leaf Collimator
OAR	Organ At Risk
OMED	Oral Morphine Equivalent Dose
PI	Principal Investigator
PR	Partial response
PRO	Patient Reported Outcome
PROMS	Patient Reported Outcome Measures
PTV	Planning Target Volume
QA	Quality Assurance
QALY	Quality Adjusted Life Year
QoL	Quality of Life
QUANTEC	Quantitative Analyses of Normal Tissue Effects in the Clinic
REB	Research Ethics Board
RINV	Radiation-Induced Nausea and Vomiting
RO	Radiation Oncologist
RT	Radiation Therapy
SAE	Serious adverse event
SF	Single Fraction
SFRT	Stereotactic Fractionated Radiotherapy
SOP	Standard Operating Procedure
SPI	Study Principal Investigator

Protocol number v12.0; 16 Apr 2024

SUPR	Simple Unplanned Palliative Radiation
VMAT	Volumetric Modulated Arc Therapy

1. Protocol Summary

Date and Version # of Protocol:	16 Apr 2024; v12.0
Sponsor: BC Cancer	Protocol Number: 18-25
Name of Study Method: Randomized Controlled Clinical Trial	Phase of Development: III
Title of Study:	
A Randomized Phase III Trial Comparing Simple Unplanned Palliative Radiotherapy versus 3D Conformal Radiotherapy for Patients with Bone Metastases.	
Study Design Overview/Rationale:	

The primary objective is to compare patient-reported Quality of Life related to Radiation Induced Nausea and Vomiting (RINV) between standard palliative radiotherapy and VMAT. Secondarily, we will assess rate of complete control of RINV, compare patient reported toxicity, and evaluate pain response. However, we hypothesize that there will be no difference in pain response between the two arms, because they are receiving the same dose.
  <pre> graph LR A[Palliative patients with bone metastases, suitable for receiving radiation therapy, and fulfill the eligibility criteria] --> B[Treating radiation oncologist decides on either 8 Gy in 1 fraction or 20 Gy in 5 fractions] B --> C[RANDOMIZATION] C --> D[Simple unplanned Palliative Radiotherapy (SUPR)] C --> E[Volumetric Modulated Arc Therapy (VMAT)] </pre>	
Trial Design and Schema	

This is a randomized, multi-centre, pragmatic phase III study in palliative patients with bone metastases.
 
Randomization will be performed on patient-level, meaning that if a patient is treated for multiple bone metastases in the same course, all will receive the same treatment technique.
	

Protocol number v12.0; 16 Apr 2024

This applies only to bone lesions, as per section 3.2. Any additional lesions to be treated will be at the RO's discretion.

Stratification: 8 Gy/1 vs 20 Gy/5

Radiation Treatment Plan (Arm 1):

Location	Dose (Gy)	Fractions	Frequency
Bone metastasis	8	1	Single fraction
Bone metastasis	20	5	Once daily

Radiation Treatment Plan (Arm 2):

Location	Dose (Gy)	Fractions	Frequency
Bone metastasis	8	1	Single fraction
Bone metastasis	20	5	Once daily

Disease Assessment:

- Patient Reported Quality of life related to RINV as scored by the Functional Living Index – Emesis (FLIE)
- Control of RINV as measured by a daily patient diary
- Patient reported pain response as measured by the Brief Pain Inventory (BPI)
- Patient reported use of medications as measured by patient diary
- Patient reported fatigue, nausea, vomiting as measured by the PRO-CTCAE
- Patient reported quality of life as measured by EORTC QLQ C-15 PAL
- Patient reported functional status as measured by PRO-ECOG
- Economic analysis as measured by EQ-5D-5L

Study Population

Patients with a clinical diagnosis of bone metastases, meeting all inclusion and exclusion eligibility criteria.

Study Objective(s):

Primary Objective

The primary objective is to compare patient-reported Quality of Life related to Radiation Induced Nausea and Vomiting (RINV) between standard palliative radiotherapy and VMAT.

Secondary Objective:

To assess rate of complete control of RINV, compare patient reported toxicity, and evaluate pain response. However, we hypothesize that there will be no difference in pain response between the two arms, because they are receiving the same dose.

Number of Subjects/Sample Size Calculations

250 subjects will be accrued

Planned Study Period:

7 Years

Inclusion Criteria:

Subjects must meet all of the following criteria to be eligible for participation in this study:

- Age 18 or older
- Able to provide informed consent
- Clinical diagnosis of cancer with bone metastases (biopsy not required)
- Currently being managed with palliative intent RT to 1-3 RT fields for bone metastases, at least one RT field (PTV) must (at least) partly lie within T11-L5 or pelvis.
- ECOG Performance Status 0-3
- Patient has been determined to potentially benefit from 8 Gy or 20 Gy
- Radiation Oncologist is comfortable prescribing 8 Gy in 1 fraction or 20 Gy in 5 fractions RT for bone metastases
- Negative pregnancy test result for women of child-bearing potential
- The baseline assessment must be completed within required timelines, prior to randomization.
- Patients must be accessible for treatment and follow-up. Investigators must assure themselves the patients randomized on this trial will be available for complete documentation of the treatment, adverse events, and follow-up.
- For simplicity of planning, expected GTV should be less than 20 cm based on radiological or clinical evidence

Protocol number v12.0; 16 Apr 2024

- Patient must be prescribed a 5-HT3 receptor antagonist (e.g. Ondansetron) as antiemetic prophylaxis prior to RT start.
- Patient is able and willing to complete the quality of life questionnaires, and other assessments that are a part of this study, via paper or using REDCap if they provide their email address on the informed consent

Waivers to the inclusion criteria will NOT be allowed.

Exclusion Criteria:

Subjects are excluded from the study if any of the following criteria apply:

- Serious medical co-morbidities precluding radiotherapy
- Clinical evidence of spinal cord compression
- Spinal cord in treatment field has already received at least >30 Gy EQD2, defined as:
$$EQD_2 = D \times ([d + (\alpha/\beta)]/[2 + (\alpha/\beta)])$$

$$D = \text{total dose given in Gy}$$

$$d = \text{dose per fraction in Gy}$$

$$\alpha/\beta = \text{dose at which the linear and quadratic components of cell kill are equal}$$
- Whole brain radiotherapy (WBRT) within 4 weeks of RT start or planned WBRT in the first 4 weeks after last RT
- Solitary plasmacytoma
- Pregnant or lactating women
- Target volume cannot be encompassed by a single VMAT isocentre
- Custom mould room requirements (shells and other immobilization that is standard-of-care is acceptable)
- Greater than two organs-at-risk requiring optimization.
- Patients requiring treatments outside standard clinical hours
- Implanted electronic device within 10 cm of the RT fields
- Prostheses in the axial plane of the target, or within 1 cm of the PTV out-of-plane
- Previous RT that requires an analysis of cumulative dose (i.e. sum plans or EQD2 calculations)
- Oral or IV contrast if the local standard-of-care requires compensation for this in planning.

Waivers to the exclusion criteria will NOT be allowed.

Concomitant Medication Restrictions or Requirements:

Required/Permitted:

- Antiemetic prophylaxis with 5-HT3 receptor antagonist (e.g. Ondansetron) prescribed before start of RT
- Analgesics can be prescribed as needed
- Concurrent hormonal therapy is allowed

Restrictions:

- Use of chemotherapy schemes containing potent enhancers of radiation damage (e.g. gemcitabine, doxorubicin, bevacizumab, adriamycin) are **discouraged within the first month after radiation**.
- WBRT in the 4 weeks before first RT and 4 weeks after last RT
- SFRT for brain metastases in the 4 weeks after last RT

Schedule of Study Assessments and Procedures:

For Schedule of Assessments refer to Section 4.8

Adverse Events Determination and Reporting:

Grade 1 toxicities such as mild fatigue, nausea, vomiting, skin irritation, pain, loss of appetite and some physical function are common and expected side effects of radiation therapy and therefore should not be reported as adverse events, if the event is documented in the subject's medical record. Only Grade 2 or higher toxicities that are possibly, probably, or definitely related to RT will be documented and reported as adverse events (AEs)/serious adverse events (SAEs).

Any **Grade 4 or 5 serious adverse event** that is definitely, probably, or possibly the result of protocol treatment must be reported to the Study PI within 24 hours of discovery. The follow-up/final report should be completed within an additional 8 days. All other SAEs (Grade 2-3) that are definitely, probably, or possibly related to treatment should be reported to the Study PI within 15 days. These should be documented in an SAE Report form and in REDCap as well.

Unanticipated events are to be reported to the Study PI within 24 hours of discovery, and to the local REB as required.

Local and non-local SAEs will be reported to the applicable REB as per their reporting guidelines.

NOTE: Conditions that are NOT considered a SAE in this protocol are not included in reporting requirements, e.g., hospitalizations for routine procedures, disease progression, or death from disease progression.

Formal Stopping Rules:

The primary objective of this study is to compare patient-reported QoL related to RINV between SUPR and VMAT. Accruing 250 patients will increase confidence in improved QoL of VMAT (i.e. lower RINV as measured by FLIE).

There is no independent data safety monitoring committee (DSMC) for this study. The DSMC will be made up of the study co-investigators. The DSMC will meet annually after study initiation to review toxicity outcomes. If any grade 3-5 toxicity is reported, the DSMC will review the case notes to determine if such toxicity is related to treatment. If the DSMC deems that toxicity rates are excessive (>25% grade 3 toxicity or >10% grade 4 or >3% grade 5 toxicity), then the DSMC can, at its discretion, recommend cessation of the trial, dose adjustment or exclusion of certain treatment sites that are deemed as high-risk for complications.

Statistical Evaluations:

Patients will be analyzed in the groups to which they are assigned (intention-to-treat).

RINV will be assessed via Functional Living Index – Emesis (FLIE) scores compared between the two arms at baseline and day 5 post start of RT

Health-Related Quality of Life (HRQoL) will be measured using the EQ-5D-5L and combined with survival outcomes to explore differences in Quality Adjusted Life Year (QALY) gains or losses between treatments

Endpoints for Evaluation:

- Patient Reported Quality of life related to RINV as scored by the Functional Living Index – Emesis (FLIE)
- Toxicity as scored by Patient Reported Outcome Measures (PROMs)
- Health-related quality of life as measured by the EQ-5D-5L and combined with survival outcomes to explore differences in QALY gains or losses between treatments

2. Introduction

2.1. Trial Rationale and Background

Bone metastases are the most common site of distant metastases and can cause severe and disabling effects, including pain, spinal cord compression and pathologic fracture^{1, 2}. These complications can greatly affect a patient's quality of life and cause immense suffering.

Radiotherapy (RT) is an effective treatment for palliative patients with painful bone metastases. It is also efficacious in preserving function and maintaining skeletal integrity, while minimizing the occurrence of adverse skeletal related events³. There is a significant amount of evidence showing that a single fraction (SF) of RT provides equivalent pain relief as multiple fractions (MF), which are associated with more acute toxicity, are less convenient for patients and costlier for the health care system^{1, 4, 5}. Therefore, SF-RT is encouraged, but 20 Gy in 5 fractions is also allowed in this study, though should be chosen only in patients with a complicated bone metastases by fracture, neurological deficit (e.g. spinal cord compression), or a large soft tissue component. In patients with advanced disease, management strategies focus on improving quality of life (QOL), rather than conventional endpoints such as survival⁶.

Rationale for Current Study

Currently, the standard of care in British Columbia for palliative patients with bone metastases is SUPR. In other jurisdictions, however, factors such as physician remuneration make other complex planning techniques more popular.

BC Cancer is publicly funded with no direct costs to patients. All RT in the province is provided by 6 centres where radiation oncologists receive an annual salary, which are independent of RT treatment technique and duration⁷. Due to the lack of financial incentive associated with a more complex RT plan, BC Cancer is a unique clinical setting to assess the use of VMAT versus SUPR⁷.

As facilities providing RT have gained more experience with VMAT and improvements to VMAT planning software have been made, the planning time required has been reduced⁸. Previously, approximately 2 weeks was required for a team at the BC Cancer to create a VMAT plan for a palliative patient with bone metastases; however, we hypothesize this can now be reduced to three days in settings with low dose prescription.

This study will allow us to determine if there is reduced toxicity associated with VMAT compared to SUPR with only a modest impact on resources. Our hypothesis is that VMAT will have reduced toxicity compared with SUPR for palliative patients with bone metastases. We also hypothesize that there will be no difference between the two arms in terms of pain response, due to the fact that the doses are equal. This hypothesis is driven by the radiobiologic rationale, which defines effective RT as the ability of radiation to induce tumour cell death while sparing normal cells.

The importance in determining if there is any benefit in terms of toxicity with VMAT compared with SUPR for palliative patients with bone metastases is obvious when consequences related to its adoption are considered. As previously discussed, although the planning time has been drastically reduced, there is still an expected modest increase in resources required to carry out a VMAT plan. For patients, the pre-treatment process of VMAT is more burdensome, i.e. patients have to wait longer before receiving VMAT as compared to SUPR, due to the increased plan complexity. Therefore, it is important to consider the patient experience in relation to the RT administration.

In summary, evidence that either supports or refutes the hypothesis that VMAT will have reduced toxicity compared with SUPR for patients with bone metastases will be helpful in guiding future practices. We are not aware of any other randomized control trials (completed or ongoing) that have addressed this issue, though a London Ontario study is randomizing patients receiving palliative lung RT to SUPR vs VMAT⁹. Due to the implications of VMAT on departmental resources and patient experience, better evidence from a randomized control trial is required before the widespread use of this technique can be justified.

2.2. Radiation Treatment Overview

2.2.1. Radiation therapy 1 - Simple Unplanned Palliative Radiotherapy (SUPR)

For this study, SUPR refers to the delivery of radiation to the treatment area with a simple technique, either two opposed fields (parallel opposed pair), or a single direct field. The entire portal is exposed to the specified dose and therefore does not spare normal tissue. This technique requires minimal calculation, and typically the dose distribution is not reviewed by the radiation oncologist or medical physics.

Adverse Events (SUPR)

In general, the adverse event profile of RT is associated with irradiation of normal tissue within the treatment field. With the dose prescribed in this study, the probability of serious adverse effects is exceedingly low¹⁰. However, fatigue, soreness, pain flare, and skin-redness in the irradiated area are relatively common adverse events. In addition, site-specific toxicity could occur, including esophagitis, nausea, or diarrhea when there is dose delivered to the GI tract. Avoiding this toxicity is a motivating factor for the study.

2.2.2. Radiation therapy 2 – Volumetric Modulated Arc Therapy (VMAT)

In order to deliver 3D Conformal Radiotherapy, a CT simulation is used to develop the treatment plan. The goal is to deliver a conformal radiation dose to the target volume with maximal sparing

Protocol number v12.0; 16 Apr 2024

of the normal tissue. VMAT (Volumetric Modulated Arc Therapy is a type of 3D conformal RT, and delivers the radiation dose more conformally than SUPR, possibly reducing acute and late toxicity¹¹⁻¹³. The disadvantages of VMAT include more complex planning and quality assurance processes compared with SUPR5. The complex planning required can be time-consuming, which can have a significant impact on departmental resources, and the wait time for the patient.

2.2.3. Sample Collection Schedule

N/A

[figure not shown]
2.3. Study Population

Patients with a clinical diagnosis of bone metastases, meeting all inclusion and exclusion eligibility criteria.

3. Trial Design

This is a randomized, multi-centre, pragmatic phase III study in palliative patients with bone metastases. Randomization will be performed on patient-level, meaning that if a patient is treated for multiple bone metastases in the same course, all will receive the same treatment technique. This applies only to bone lesions, as per section 3.2. Any additional lesions to be treated will be at the RO's discretion.

Patients will be stratified by treatment dose of either 8 Gy in a single fraction or 20 Gy in 5 fractions.

3.1. Study Objectives and Endpoints

3.1.1. Objectives

Primary Objective

The primary objective is to compare patient-reported Quality of Life related to Radiation Induced Nausea and Vomiting (RINV) between standard palliative radiotherapy and VMAT.

Secondary Objective(s)

To assess rate of complete control of RINV, compare patient reported toxicity, and evaluate pain response. However, we hypothesize that there will be no difference in pain response between the two arms, because they are receiving the same dose.

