3.1.2. Endpoints

Primary Endpoint:

Patient Reported Quality of life related to Radiation Induced Nausea and Vomiting (RINV) as scored by the Functional Living Index – Emesis (FLIE) at day 5 post RT start.

Secondary Endpoints

Primary efficacy outcome

- Control of RINV measured by a daily patient diary (day 1-5)

Secondary Patient Reported Outcome Measures (PROMs)

- Pain flare measured by the Brief Pain Inventory (BPI)
- Diary of medication use (specifically anti-emetics)
- PRO-CTCAE T11 – L5 & Pelvis:
 - Decreased appetite
 - Nausea
 - Vomiting
 - Diarrhea
 - Radiation skin reaction
 - Pain flare
 - Fatigue
- Pain response assessed by the Brief Pain Inventory.
- Proportion of patients who receive treatment within 1 day, 2 days, 3 days, 4 days, 5 days, or more than 5 days,
- Toxicity assessed at baseline and follow-up
- Quality of Life: single item from EORTC QLQ C-15 PAL: How would you rate your overall quality of life during the past week
- Performance status: as reported by patient with PRO-ECOG
- Cost effectiveness of SUPR vs. VMAT assessed by EQ-5D-5L

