5.5. Subject Compliance/Deviations

Subject compliance, such as attending study visits and completing questionnaires, will be monitored via REDCap. If any visits are not completed, investigator or delegate must call and conduct follow-up over the telephone. Missed visits must be documented in the deviation log.

Deviations to eliminate immediate hazards to study subjects must be reported to the Study PI immediately upon discovery and to the REB within 7 calendar days. All other reportable deviations must be reported to the Study PI immediately, however to the REB within 15 calendar days. See section **12.1.2 Protocol Deviations** for a list of deviations.

Protocol number v12.0; 16 Apr 2024

6. Dose Modifications

N/A.

7. Assessment of Efficacy

Treatment Response Evaluation

FLIE:

Scores on all individual questions will be weighted equally, reversed if required and summed to create an overall FLIE score. Minimum score and maximum score will be 18 and 126 respectively. A low score is favorable, reflecting less nausea and vomiting.

The paper version of the FLIE is a 7-point Likert-scale. Patients' responses will be rounded to the closest point on the scale for entry in the digital database. I.e. if the response is 1.4, this will be rounded to 1. If the response is 1.5, it will be rounded to 2.

RINV:

Complete control: no increased episodes of nausea or vomiting with no increased use of anti-emetic medication from baseline

Partial control: 1-2 increased episodes of nausea or vomiting with no increased use of anti-emetic medication compared to baseline

Uncontrolled response: 3 or more increased episodes of nausea or vomiting, or increased use of anti-emetic medication from baseline

Overall control: includes complete and partial control

Pain:

Complete response: pain score of 0 at treated site with no increase in analgesic intake (stable or reducing analgesics in daily oral morphine equivalent (OMED).

Partial response: pain reduction of 2 or more at the treated site on a scale of 0 to 10 without analgesic increase, or analgesic reduction of 25% or more from baseline without an increase in pain.

Pain progression: Increase in pain score of 2 or more above baseline at the treated site with stable OMED, or an increase of 25% or more in OMED compared with baseline with the pain score stable or 1 point above baseline.

Indeterminate response: Any response that is not captured by the complete response, partial response or pain progression definitions¹⁴.

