9.1. Statistical Methods

Patients will be analyzed in the groups to which they are assigned (intention-to-treat). All analyses will be done using t-tests between the average scores of the two arms.

RINV will be assessed via Functional Living Index – Emesis (FLIE) scores compared between the two arms at baseline and day 5 post start of RT

Health-Related Quality of Life (HRQoL) will be measured using the EQ-5D-5L and combined with survival outcomes to explore differences in Quality Adjusted Life Year (QALY) gains or losses between treatments

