9.2. Planned Subjects Enrolled

The primary outcome is Functional Living Index – Emesis (FLIE) score compared between the two arms at day 5 post start of RT. We expect patients in the SUPR arm to have a mean FLIE score of 36, 5 days post start of RT¹⁷. We anticipate that VMAT will have a much lower RINV impact (i.e. less decline in FLIE) and for the purpose of this study will hypothesize that the FLIE will be approximately 28. The standard deviation used for sample size calculation was 16.

Sample size was calculated with these FLIE scores. With alpha Type I error set at 0.05 and power set at 0.9, with a dropout rate of 30%, we calculated a conservative sample size of 250 patients. This dropout rate of 30% is a conservative number. We will collect patient demographics and if there is an indication that bias is being introduced because of dropout, we will consult with a statistician.

Our most important secondary outcome (primary efficacy outcome) is radiation induced nausea and vomiting (RINV) which occurs in 60% of patients who receive RT to the lower spine or pelvis^{17, 18}. Using the sample size of 250 patients (see above), this study has a power of 0.8 to detect a 25% difference in RINV (from 60% to 35%) with alpha Type I error set at 0.05 and a dropout rate of 20%. As outlined in the table below, if RINV difference is lower, or higher our power will be lower and higher, respectively.

Health-Related Quality of Life (HRQoL) will be measured using the EQ-5D-5L and combined with survival outcomes to explore differences in Quality Adjusted Life Year (QALY) gains or losses between treatments¹⁹.

Approximate sample size required

RINV 60% to 50% 1600

RINV 60% to 40% 400

Protocol number v12.0; 16 Apr 2024

RINV 60% to 35%	250
RINV 60% to 30%	175
RINV 60% to 20%	90

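### The leading secondary endpoint, diary-based RINV control, is not carried through from objective to analysis: complete control is the objective, but no category is named for the endpoint or the power, and the only stated test does not fit a proportion

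*Combined protocol and SAP*

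**What the plan says.** Section 9.2 calls RINV the most important secondary outcome. Five places bear on how it is measured and analysed.

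- **Objective (3.1.1, and the summary):** "To assess rate of complete control of RINV, compare patient reported toxicity, and evaluate pain response". This names complete control.
- **Endpoint (3.1.2, repeated in 10.1.3):** "Control of RINV measured by a daily patient diary (day 1-5"). The word complete is absent and no category is chosen.
- **Definitions (section 7):** complete control means no extra episodes and no extra anti-emetic use. Partial control means one or two extra episodes and no extra anti-emetic use. Uncontrolled means three or more extra episodes, or any extra anti-emetic use. Then: "Overall control: includes complete and partial control". Section 7 does not say which category is compared between arms.
- **Methods (9.1):** all analyses are to be t-tests of the arms' average scores, and "RINV will be assessed via Functional Living Index – Emesis (FLIE) scores compared between the two arms". No method for a proportion is given.
- **Power (9.2):** "this study has a power of 0.8 to detect a 25% difference in RINV (from 60% to 35"%). The calculation takes over the total of 250 from the primary endpoint, puts alpha at 0.05 and allows for 20% dropout. The 60% is described as the rate at which RINV occurs and is not linked to any section 7 category. A table of approximate sample sizes follows.

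**The concern.** A patient with one or two extra episodes and no extra anti-emetic use fails complete control but succeeds on overall control. That group changes sides with the definition, so the event count and the power change too. A patient with no extra episodes but more anti-emetic use is uncontrolled under section 7, yet would not obviously be someone in whom RINV occurred as section 9.2 uses the term.

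The objective settles the category in principle. The endpoint list, the methods and the power statement do not repeat it, and the methods contain no test for a proportion. The analyst therefore has to supply both the category and the method for the endpoint the plan ranks just below the primary. In an open-label trial these choices are better fixed in writing before the data are examined.

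**Working it through.** **Inputs.** Total 250 and 20% dropout (section 9.2), 1:1 allocation (section 3.2), rates 0.60 and 0.35, alpha 0.05 (section 9.2). Sidedness is not stated; two-sided is assumed. Evaluable patients: 250 × 0.80 = 200, or n = 100 per arm.

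**Formula.** Power = Φ{(|p1 − p2| − 1.96·√[2p̄(1 − p̄)/n]) / √[(p1(1 − p1) + p2(1 − p2))/n]}, with p̄ = (p1 + p2)/2 and no continuity correction.

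**The plan's own figure.** With p̄ = 0.475, the null standard error is √(0.49875/100) = 0.0706 and the alternative standard error is √(0.4675/100) = 0.0684. Then (0.25 − 1.96 × 0.0706)/0.0684 = 1.63, and the power is 0.949. The stated 0.80 is not reproduced. A one-sided test gives 0.975. Applying the 30% dropout that section 9.2 uses for the primary endpoint (175 evaluable) gives 0.919. Power of 0.80 needs only 62 per arm: 124 evaluable, or 124/0.80 = 155 enrolled.

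**The plan's table.** It matches 95% power, two-sided, with evaluable total divided by 0.80:

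| RINV | Evaluable total at 95% power | ÷ 0.80 | Plan's table |
|---|---|---|---|
| 60% to 50% | 1282 | 1603 | 1600 |
| 60% to 40% | 320 | 400 | 400 |
| 60% to 35% | 202 | 253 | 250 |
| 60% to 30% | 138 | 173 | 175 |
| 60% to 20% | 72 | 90 | 90 |

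So the table agrees with the recomputed 0.95, and the 0.80 in the text agrees with neither.

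**Power by definition, 100 evaluable per arm.** The partial-control shares below are assumptions, because the documents give none.

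1. If 60% against 35% is failure of complete control, complete control is 40% against 65%. The two are complements and power is unchanged at 0.949.
2. If 60% against 35% is failure of complete control but overall control is analysed, the event is uncontrolled RINV. Suppose the same share of failures in both arms is only partial control. With a quarter, the rates are 0.75 × 60% = 45% against 0.75 × 35% = 26.25%, and power is 0.795. With a half, they are 30% against 17.5%, and power is 0.547.
3. If 60% against 35% already means uncontrolled RINV but complete control is analysed, suppose a share g of the remaining patients has partial control. With g = 0.2, the rates are 60 + 0.2 × 40 = 68% against 35 + 0.2 × 65 = 48%, and power is 0.822. With g = 0.4, they are 76% against 61%, and power is 0.628.

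**The case against.** The strongest reply is that the objective already chooses complete control, section 7 defines it exactly, and no passage makes overall control the between-arm comparison. On that view, control of RINV in the endpoint list is only a short title. Much of this stands, and it is why the remedy adopts complete control. It does not supply a test for a proportion, and it does not say what the 60% and 35% measure.

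Four stronger readings are tempting, and the documents do not support them.

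- **FLIE as a competing definition of this endpoint.** A reader might infer this from section 9.1. Sections 3.1.2, 5.2.1.1, 9.2 and 10.1.1 all tie FLIE at day 5 to RINV-related quality of life, and 3.1.2 and 9.2 make it the primary endpoint. The 9.1 sentence is best read as the primary comparison loosely labelled RINV. What remains is that the diary endpoint has no analysis of its own.
- **The 60% cannot be failure of complete control.** It comes from cited sources that cannot be checked here. Whether it counts anti-emetic use is unknown, so the equation can be stated as an assumption but neither asserted nor ruled out.
- **The episode cut-offs leave the endpoint undefined because they do not say per day or over five days.** For complete control the unit is irrelevant: zero extra episodes on every day is the same as zero in total. It only moves patients between partial and uncontrolled.
- **Ambiguity costs a large amount of power against what the plan claims.** Measured from the plan's stated 0.80, the quarter scenario costs almost nothing. Only larger assumed shares give a material loss.

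The concern about choosing a definition late is also tempered by the blinding of assessors and analysts to arm identity (section 3.2) and the duty to justify deviations from the statistical plan (section 9.3). Neither selects the category.

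**Conclusion.** The inconsistency is real but limited. The objective specifies complete control; the endpoint list, the t-test rule and the power statement do not carry it through. Two parts need no assumption about partial control: t-tests of average scores do not suit a diary proportion, and the stated power of 0.80 disagrees with its own inputs, which give about 0.95 (two-sided, 20% dropout, normal approximation). That error is in the conservative direction, so the trial is not undersized for a 60% to 35% contrast. The loss of power under overall control, to about 0.80 or 0.55, is illustrative and rests on assumed partial-control shares of a quarter or a half. The sponsor should make the change because of the rank the plan gives this endpoint. The primary FLIE comparison is unaffected.

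**What to change.** - **3.1.2 and 10.1.3:** name the endpoint as the proportion of patients with complete control, as defined in section 7, over diary days 1-5. Make overall control descriptive.
- **9.1:** keep the FLIE sentence, because it is the only statement of the primary comparison in that section, but relabel it as the primary endpoint, RINV-related quality of life. Exempt the diary endpoint from the t-test rule. Compare complete-control proportions as a risk difference with 95% confidence interval, stratified by 8 Gy in 1 against 20 Gy in 5.
- **9.2:** state that 60% against 35% is assumed to be failure of complete control, and check the cited rate against that definition. Replace 0.80 by about 0.95 for 250 patients, 20% dropout and two-sided 0.05. Say that power for overall control depends on the unknown share of failures that are only partial control.

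The cost is protocol and analysis-plan wording before database lock, with no new data. The small downside is that overall control can no longer be presented as the main RINV result.
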